8 STUDY ENDPOINTS

8.1 Primary Endpoints

The primary endpoints are measures of vaping topography [(per-puff volume, inter-puff interval, peak flow rate, puff count, total volume (sum of volumes across all puffs)], which are treated as quantitative outcomes and will be summarized by:

- Condition (flavor or nicotine composition) and,
- Bout (directed or ad-lib) using the appropriate descriptive statistics.

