10 STUDY INTERVENTION

Participants will vape twice per session – once directed and once ad lib. In the directed bout, participants are instructed to take a 4 second puff on the device every 60 seconds until a total of 8 puffs are completed. In the ad lib bout, participants are free to puff as they like for a defined 15 minute period.

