19.1 Sample Size Determination

The planned sample size is n=72 evaluable patient, who are expected to complete 7 potential sessions, for a total of 504 observations.

However, we anticipate an attrition rate of 5-10% per session and the table below provides expected sample sizes under differing rates of attrition:

Session		1	2	3	4	5	6	7
Subjects Completed	5% Attrition	72	68	65	62	59	56	53
	10% Attrition	72	65	58	52	47	43	38
	5% 1-3 and 10% in 4-7	72	68	65	58	53	47	43

A conservative sample size calculation is based on comparing any two flavors or nicotine formulations using a two-sided paired t-test. The minimum expected sample size per combination is expected to be between 38 and 53; which provides 80% power (at $\alpha=0.05$) to detect a difference of at least 0.47 and 0.39 standard deviations. Since the actual models used in the analysis will account for additional sources of variability and will borrow information across sessions, the actual detectable effect sizes may be larger.

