19.4 Primary Analysis

The primary objective is to evaluate the influence of:

Roswell Park Protocol No.: I-3234822

- a. tobacco flavoring composition on vaping topography
- b. synthetic vs. tobacco derived nicotine on vaping topography

The primary endpoints are measures of vaping topography, which are treated as quantitative outcomes and will be summarized by condition (flavor or nicotine composition) and bout (directed or ad-lib) using the appropriate descriptive statistics.

Using data from sessions 1-5, each endpoint will be modeled as a function of flavoring (own, none, and 3 commercial flavors), bout (directed or ad-lib), their two-way interaction, and random subject and site effects using a linear mixed model. Tests about the appropriate contrasts of model estimates will be used to compare:

- i) mean differences between flavors within a type of bout,
- ii) mean differences between bouts within a flavor,
- iii) effects of bout (ad lib – directed) between flavors,
- iv) effect of flavor between bouts.

Using data from sessions 6 & 7, each endpoint will be modeled as a function of nicotine composition (synthetic vs. tobacco derived), bout (directed or ad-lib), their two-way interaction, and random subject and site effects using a linear mixed model. Tests about the appropriate contrasts of model estimates will be used to compare:

- i) mean differences between composition within a type of bout,
- ii) mean differences between bouts within a composition,
- iii) effects of bout (ad lib – directed) between compositions,
- iv) effect of composition between bouts.

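### For puff count and inter-puff interval, one mixed model over both bouts gives wrong standard errors under the default covariance, because the directed bout holds both endpoints nearly constant

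*Combined protocol and SAP*

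**What the plan says.** Section 8.1 names five primary endpoints: "per-puff volume, inter-puff interval, peak flow rate, puff count, total volume". Section 19.4 models each of them on both bouts together, as a function of liquid (five levels in the flavor model, two in the nicotine model), bout, "their two-way interaction, and random subject and site effects using a linear mixed model". It then lists four kinds of contrast, unranked: liquids within a bout, bouts within a liquid, the bout effect compared between liquids, and the liquid effect compared between bouts.

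The interaction frees the means only. Section 19.4 gives no residual covariance structure, subject-by-bout effect, robust standard error or separate analysis by bout.

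Section 10 describes two very different bouts. The directed regimen reads: "participants are instructed to take a 4 second puff on the device every 60 seconds until a total of 8 puffs are completed". The free regimen, by contrast, reads: "In the ad lib bout, participants are free to puff as they like for a defined 15 minute period". Section 17.1 lets a participant stop using the product at any time, so the directed count is nearly constant rather than strictly constant.

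**The concern.** Puff count and inter-puff interval are outcomes in the ad lib bout and instructions in the directed bout. A model with one subject intercept and one residual variance averages a bout that varies freely with one that hardly varies, and uses the result as the error term for both. It also credits each subject with the same deviation in both bouts, although a heavy puffer cannot show that in a bout fixed at 8 puffs. The misfit goes into the residual.

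These two errors act in opposite directions on the ad lib contrasts. Averaging in the quiet bout makes the residual too small, and the misplaced subject effect makes it too large. Which one wins depends on how consistent subjects are across sessions. The comparison of liquids within a bout bears directly on both primary objectives, so its error rate would rest on a nuisance parameter that the plan does not state. A larger sample does not help, because the true and reported standard errors shrink together.

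**Working it through.** **The plan's own figure.** Section 19.1 rests on "comparing any two flavors or nicotine formulations using a two-sided paired t-test". On the evaluable number it says: "The minimum expected sample size per combination is expected to be between 38 and 53". On the detectable difference at those two sizes it says: "which provides 80% power (at $\alpha=0.05$) to detect a difference of at least 0.47 and 0.39 standard deviations".
- Attrition: 72 × 0.90^6 = 38.3 and 72 × 0.95^6 = 52.9, matching 38 and 53.
- Noncentral t at 80% power: 0.467 SD (n=38) and 0.392 SD (n=53). Power at the stated 0.47 and 0.39 is 80.5% and 79.6%.

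These figures reproduce. They rest on a paired t-test, so the covariance question does not touch them.

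**Inputs for the model check.** F is the number of liquids in the model (Section 19.4: 5 or 2). Scale the ad lib variance to 1, with subject part ICC and residual part 1−ICC. The directed SD is k times the ad lib SD, and ρ is the correlation of a subject's effects in the two bouts. The documents give none of ICC, k or ρ, so all three are assumptions. Data are taken as balanced.

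**Formulas.**
- Variance of the difference between a subject's two effects: V = ICC × (1 + k² − 2ρk).
- Expected residual variance of the one-intercept model: M = (1−ICC)(1+k²)/2 + F × V / [2(2F−1)].
- Reported/true SE of a liquid contrast: ad lib R = √[M/(1−ICC)]; directed R/k.
- Type I error ≈ 2[1 − Φ(1.96 × ratio)].

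**Worked case**, k=0, F=5, ICC 0.5: M = 0.25 + 5 × 0.5/18 = 0.389. R = √(0.389/0.5) = 0.882. Type I error = 2[1 − Φ(1.729)] = 8.4%.

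**Puff count and interval, ad lib contrast, ρ = 0.6** (ratio, then type I error):

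| ICC | Flavor, k=0.02 | Flavor, k=0.33 | Nicotine, k=0.02 | Nicotine, k=0.33 |
|---|---|---|---|---|
| 0.3 | 0.79, 12.4% | 0.80, 11.7% | 0.80, 11.7% | 0.81, 11.2% |
| 0.5 | 0.88, 8.5% | 0.87, 8.9% | 0.91, 7.5% | 0.89, 8.1% |
| 0.7 | 1.06, 3.7% | 1.01, 4.8% | 1.12, 2.8% | 1.05, 3.9% |
| 0.85 | 1.43, 0.5% | 1.30, 1.1% | 1.53, 0.3% | 1.38, 0.7% |

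The ratio passes through 1 between ICC 0.60 and 0.70. For directed contrasts in the flavor model, the reported SE is 2.4 times (k=0.33, ICC 0.3) to 71 times (k=0.02, ICC 0.85) the true SE. Rejection under no effect is then about 0%.

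**Simulation.** Balanced null trials (4,000 per setting, n=50, five liquids, k 0.02-0.33, ρ 0.6) gave ad lib type I error of 11-13%, 8-10%, 4-5% and 0.6-1.5% at ICC 0.3, 0.5, 0.7 and 0.85. With k=0, modeling the ad lib bout on its own gave 4.7-5.3% in every setting tried. A small set of fits in standard mixed-model software (12 per setting, k=0) gave ratios of 0.75, 0.86 and 1.22 at ICC 0.2, 0.5 and 0.8, against 0.75, 0.88 and 1.27 from the formula.

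**At the crossover.** Take F=5, ICC 0.64, k=0.02, ρ=0.6. Then V = 0.625 and M = 0.354, and the ad lib liquid contrast is close to nominal.
- Bouts within a liquid: true variance is proportional to V + (1−ICC)(1+k²) = 0.985, reported 2M = 0.707. Ratio √(0.707/0.985) = 0.85, type I error 9.7%.
- Bout-by-liquid: true 2(1−ICC)(1+k²) = 0.720, reported 4M = 1.415. Ratio 1.40, type I error 0.6%.

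**The other endpoints.** The directed bout sets puff duration and timing, not volume or flow. With assumed k of 0.5-1, ρ of 0.4-1 and ICC of 0.5-0.7 (F=5), the ratio is 0.83-1.33 for ad lib and 1.00-2.17 for directed contrasts. It is exactly 1.00 when k=1 and ρ=1.

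**The case against.** The strongest reply is that the single residual variance is not in the text. Section 19.4 is silent on residual structure, and Section 19.1 says that the fitted models will allow for further sources of variability. A careful analyst could fit bout-specific variances without departing from the plan. This stands in part: the pooled residual is a default reading. But the only random effects stated are subject and site, and nothing elsewhere commits the analysis to more. A covariance chosen after seeing the data would be a post hoc choice on primary tests.

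Four stronger readings are tempting, and the documents do not support them.
- That all five primary endpoints have wrong standard errors. The instruction fixes two of them. It reaches total volume only through the count, and for per-puff volume and peak flow no error can be shown.
- That ad lib tests give too many false positives. The direction reverses with the ICC, which is not given.
- That directed tests lack power. Rejection of about 0% was found under no liquid effect and is not a power figure. For two endpoints set by instruction there is little liquid effect to detect in any case.
- That the sample size is undermined. It is not.

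It is also fair to say that Section 1.1 names no bout, so calling within-bout contrasts the main ones is an interpretation. The descriptive summaries by condition and bout in Sections 8.1 and 19.4 should reveal the near-constant directed values. They would not change the prespecified tests.

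**Conclusion.** The point holds for puff count and inter-puff interval. If the stated random effects are fitted with the default residual, the standard errors for these two primary endpoints are wrong. The ad lib liquid contrast is nominal only if the ICC happens to fall at the crossover, and even there other planned contrasts are not. The near-zero directed variance follows from the protocol. The size of the error does not: it rests on the assumed ICC, SD ratio and between-bout correlation, and on balanced data, whereas Section 19.1 expects 5-10% attrition per session. For the remaining three endpoints, the supportable finding is that the covariance is unspecified. SHOULD-FIX, moderate confidence.

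**What to change.** In Section 19.4:
- For puff count and inter-puff interval, test liquid effects in the ad lib bout only, and report the directed values as adherence checks.
- For per-puff volume, peak flow rate and total volume, prespecify bout-specific residual variances with correlated subject-by-bout effects, or compare liquids in a separate model for each bout.

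Section 19.5 reuses these models for the sensory measures, so it should say which covariance applies there.

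The cost is wording and a few more covariance parameters to estimate. Directed-bout and bout-by-liquid tests are given up for puff count and interval. No new data are needed, and Section 19.1 stays as it is.

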19.5 Secondary Analysis

The models described above will be used to evaluate the effect of flavoring and nicotine formulation on sensory measures.

20 PROVISIONS TO MONITOR THE DATA TO ENSURE THE SAFETY OF SUBJECTS

Subjects will be monitored for safety during product use sessions by trained laboratory staff. Participants are able to use the study products ad lib and can stop product use at any time without being withdrawn from the study completely. Subjects will be given phone numbers for research associates and supervising physicians to call if there are adverse effects or other study-related problems. Subjects will be advised that if they have any adverse effects and/ or wish to stop participating in the study for any reason, they are free to do so.

The data collected from this study will be organized by a unique identification number assigned to the participant so that their identity will be available only to project staff and will remain completely confidential. The clinical study coordinator, study staff, and PI of the study will have access to the data records. All study records will be kept electronically in Roswell Park Comprehensive Cancer Center maintained and secured equipment. Any data, specimens, forms, reports, and other records that leave the site will be identified only by a participant identification number (Participant ID, PID) to maintain confidentiality. All records will be kept in a limited

Roswell Park Protocol No.: I-3234822

access environment. All computer entry and networking programs will be done using PIDs only. Information will not be released without written authorization of the participant.

21 VULNERABLE POPULATIONS

N/A

22 COMMUNITY-BASED PARTICIPATORY RESEARCH

N/A

23 SHARING OF RESULTS WITH SUBJECTS

Positive pregnancy test results will be shared with participants where applicable.

24 SETTING

All study sessions will take place in The Health Behavior Human Exposure Lab located at Roswell Park Comprehensive Cancer Center or an equivalent laboratory environment at the University of Rochester Medical Center (URMC). The research team will identify and recruit potential participants from the Western New York region.

25 PROVISIONS TO PROTECT THE PRIVACY INTERESTS OF SUBJECTS

Any data, specimens, forms, reports, video recordings, and other records that leave the site will be identified only by a participant identification number (Participant ID, PID) to maintain confidentiality. All records will be kept in a limited access environment. All computer entry and networking programs will be done using PIDs only. Information will not be released without written authorization of the participant.

26 RESOURCES AVAILABLE

Investigators on this protocol have the education and research training and experience to conduct this study safely and appropriately. All data and specimen collection will be done by trained clinical research coordinators, research associates or certified phlebotomists working on this study.

All study procedures at RPCI will be performed in the:

Health Behavior Human Exposure Lab
Gratwick Basic Science Building (GBSB)
Laboratory location: 3rd Floor, Room 3920
Laboratory [contact]

The laboratory is 10' x 10.5" x 11'8" space equipped with a sink, multiple infusion chairs, and an Axis Communications video camera. In addition, the laboratory also has specialized mechanical exhausts and ducts designed to keep the room under negative air pressure at all times.

University of Rochester Medical Center (URMC) will be an additional study site. The site PI is [name]. A reliance agreement will be entered wherein Roswell Park is the IRB of record.

Roswell Park Protocol No.: I-3234822

[name] (SUNY Buffalo) will be providing technical assistance on topography device use, troubleshooting, and interpretation. [name] will be acting primarily in an advisory capacity and will not have access to any data containing PHI.

27 PRIOR APPROVALS

Not applicable.

28 COMPENSATION FOR RESEARCH-RELATED INJURY

If the subject believes they have been injured as a direct result of their participation in this research study, they will be advised to notify the Roswell Park Patient Advocate at [contact] or the Study Doctor at [contact].

Medical diagnosis and treatment for the injury will be offered, and a determination will be made regarding appropriate billing for the diagnosis and treatment of the injury. A financial counselor [contact]) will be able to provide an explanation of coverage and to answer questions the subject may have regarding study related billing.

The subject is not prevented from seeking to collect compensation for injury related to malpractice, fault, or blame on the part of those involved in the research.

29 ECONOMIC BURDEN TO SUBJECTS

Participants will be responsible for transportation to and from the research site and any costs that might entail. The remainder of the study will be conducted at no financial cost or obligation to the participant.

30 CONSENT PROCESS

The Roswell Park SOP: Informed Consent Process for Research (HRP-090) will be followed.

Consent will be obtained at Session 1 before any tests, procedures, or questionnaires (other than eligibility screeners) are administered in the tobacco research laboratory.

Each participant shall read, understand, and sign an instrument of informed consent prior to performance of any study-specific procedure. It is the responsibility of the investigator to ensure that the participant is made aware of the investigational nature of the treatment and that informed consent is given. Consent will be obtained at the beginning at the first visit prior to any data collection. Research staff will guide participants through the consent form, provide the participant time to read the consent form, and answer any questions. Participants will verbally consent, sign the consent form (physically or electronically), and show the consent form to research staff to ensure it is filled out correctly. The research staff will sign their copy of the consent form upon verbal consent and demonstration of signing the consent form. The signed consent form (or a photograph of signed consent) will then be returned to research staff through secure email or drop off/pick up.

Consent may be obtained through the REDCap (Research Electronic Data Capture) system used for data collection. REDCap is a secure web-based application that supports data capture and management for research studies. The Investigator and Research Associate will design the study specific consent and upload the most recent CRS version to the REDCap system. A secure link will be sent to each participant prior to the start of the study. Research staff will guide the

Roswell Park Protocol No.: I-3234822

participant form, provide time to read the consent, and answer any questions. Participants will be able to electronically sign, date, and submit the consent in real-time. Once the consent is submitted, it is automatically saved on Roswell Park protected servers.

In the event of REDCap being inaccessible for a study visit, pdf files or paper copies of the consent will be administered, and the participant will be able to either sign and return or submit a photo of the signed copy as stated above.

All RedCap consent files will be stored on protected servers at Roswell Park. Access to this folder is restricted to authorized users. Standard protocols for data encryption when using laptops and USB drives will be followed.

The Investigator is responsible for the retention of the participant log and participant records; although personal information may be reviewed by authorized persons, that information will be treated as strictly confidential and will not be made publicly available. The investigator is also responsible for obtaining participant authorization to access medical records and other applicable study specific information according to Health Insurance Portability and Accountability Act regulations (where applicable).

This study will be conducted in compliance with all applicable laws and regulations of the state and/or country and institution where the participant is treated. The clinical trial should be conducted in accordance with the ethical principles embodied in the Belmont Report: Ethical Principles and Guidelines for the Protection of Human Subjects of Research, consistent with good clinical practice and the applicable regulatory requirements and according to the guidelines in this protocol, including attached appendices.

31 PROCESS TO DOCUMENT CONSENT IN WRITING

The Roswell Park SOP: Written Documentation of Consent (HRP-091) will be followed.

Consent will be obtained at Session 1 before any tests, procedures, or questionnaires (other than eligibility screeners) are administered in the tobacco research laboratory.

The Investigator (or IRB specified designee) is responsible for obtaining written consent from each participant in accordance with GCP guidelines using the approved informed consent form, before any study specific procedures (including screening procedures) are performed. The informed consent form acknowledges all information that must be given to the participant according to applicable GCP guidelines, including the purpose and nature of the study, the expected efficacy and possible side effects of the s(s), and specifying that refusal to participate will not influence further options for therapy. Any additional information that is applicable to the study must also be included. Additional national or institutionally mandated requirements for informed consent must also be adhered to. The participant should also be made aware that by signing the consent form, processing of sensitive clinical trial data and transfer to other countries for further processing is allowed.

The Investigator or designee shall provide a copy of the signed consent form to the participant and the signed original shall be maintained in the Investigator File. A copy of the signed consent form must be filed in the participant file. At any stage, the participant may withdraw from the study and such a decision will not affect any further treatment options.

Roswell Park Protocol No.: I-3234822

32 DRUGS OR DEVICES

During each visit, participants will be asked to use E-liquids (unflavored, tobacco flavor). The primary psychoactive ingredient in all products is nicotine. All products are currently available for commercial purchase and will be purchased by the research team either online or at local stores (e.g., tobacco/vape shops, convenience store). These nicotine-containing products will be stored in a cool, dark location in laboratories or offices that are locked and only accessible to those with a key. When participants are randomized to a condition, the laboratory staff session will retrieve only the product needed for the individual session and will bring it directly to the participant in the lab.

Under no circumstances will the Investigator allow the study product to be used in a manner other than as directed by this protocol.

34 APPENDICES/ SUPPLEMENTS

Appendix A Recruitment Materials (Print Ad Copy)

**RESEARCH PARTICIPANTS
NEEDED**

Researchers at Roswell Park are searching for **current daily vapers to participate in a laboratory research study.**

Participation involves up to 7 sessions that last about 1 hour each.

Must be 21+ years old daily vaper to participate.

**Participants will be compensated
for their time.**

If interested, please contact [[contact] or [contact] and ask for the TOPOG study

Appendix B Study Screeners

Appendix B1: Core Eligibility Screener

Core Eligibility Screener

Name: _____

Preferred Phone Number _____

Type of phone: _____ Land Line _____ Mobile

If Mobile Phone, may we text you? _____ yes _____ no _____ only if necessary

1. Do you currently use tobacco products? By currently, we mean any use at all in the last month (30 days)

Yes (please proceed to question 2)
 No (please proceed to question 3)

2. Which tobacco products have you used in the past 30 days? Please check all that apply.

Cigarettes
 Cigars
 Cigarillos
 Clove Cigarettes
 Herbal Cigarettes
 Bidis
 Pipe Tobacco
 Roll Your Own
 Chewing Tobacco
 Moist Snuff
 Snus
 E-Cigarettes
 Vapes
 JUUL
 Nicotine pouches (i.e.: Zyn, On!, Velo)
 Nicotine gummies
 Nicotine gum
 Nicotine lozenges
 No products. I do not use tobacco or nicotine products.
(Please proceed to question 6)

3. Have you used tobacco or nicotine products in the past?

Yes (please proceed to question 4)
 No (please proceed to question 6)

Roswell Park Protocol No.: I-3234822

4. What products did you use? Please check all that apply.

- Cigarettes
- Cigars
- Cigarillos
- Clove Cigarettes
- Herbal Cigarettes
- Bidis
- Pipe Tobacco
- Roll Your Own
- Chewing Tobacco
- Moist Snuff
- Snus
- E-Cigarettes
- Vapes
- JUUL
- Nicotine pouches (i.e.: Zyn, On!, Velo)
- Nicotine gummies
- Nicotine gum
- Nicotine lozenges

5. How long ago did you quit smoking?

- More than a year ago
- Less than a year ago
- Less than 6 months ago
- Less than a month ago

6. Have you used any Nicotine Replacement medication such as the patch, gum, lozenge, spray, or inhaler in the past 30 days?

- Yes
- No

7. Do you smoke cigarettes some days or every day?

- Some Days
- Every Day
- Not at all

8. How many cigarettes do you smoke per day? Please enter a number.

9. How long have you been smoking?

- More than 1 year
- Less than 1 year
- Not at all

Roswell Park Protocol No.: I-3234822

10. Have you tried to quit smoking in the past 30 days?
(more than a 24 hour time period without smoking)

- Yes
- No
- Not a smoker

11. Are you seriously thinking of quitting smoking?

- Yes, within the next 30 days
- Yes, within the next 6 months
- No, not thinking of quitting
- Not a smoker

12. How would you describe your gender identity? (for demographics purposes, only)

- Male
- Female
- Trans-male
- Trans-female
- A different gender identity not listed above

13. What is your age? Please enter a number (years).

14. Please describe your overall health.

- Excellent
- Very Good
- Good
- Fair
- Poor

15. Please describe your overall mental health.

- Excellent
- Very Good
- Good
- Fair
- Poor

16 MEN. How many times in the past year have you had 5 or more alcoholic drinks in a day?
Please enter the number below.

16 WOMEN. How many times in the past year have you had 4 or more alcoholic drinks in a day?
Please enter the number below.

Roswell Park Protocol No.: I-3234822

17. Are you currently involved in any other Roswell Park research studies?

Yes
 No

End Script: Thank you for completing the Roswell Park Cancer Institute, Health Behavior Core Screener. Congratulations on your preliminary eligibility! We currently have several ongoing studies and want to place you with the best one based on your eligibility.

1. Would you like to be called for study-specific eligibility?

Yes (please proceed to question 2)
 No, I do not wish to leave a phone number (please proceed to question 6)

2. Please enter your name.

3. Please enter your phone number, starting with the area code.

4. What day(s) would be the best to reach you? Please check all that apply.

Monday
 Tuesday
 Wednesday
 Thursday
 Friday
 Saturday
 Sunday

5. What time of day would be best to reach you? Please check all that apply.

Morning (8am – 12pm)
 Afternoon (12pm – 4pm)
 Evening (4pm – 8pm)

6. Would you like to be emailed for study-specific eligibility?

Yes (please proceed to question 7)
 No, I do not wish to leave an email address (please proceed to question 9)

7. Please enter your name.

8. Please enter your email address.

9. For more information on study-specific eligibility, please call the Roswell Park Cancer Institute, CRoFT Study Line at [name] or email [contact]. Thank you for your time and have a great day.

